18.2.3 Confirmatory Secondary Endpoints

NA

18.2.4 Supportive Secondary Endpoints

For patients that develop inhibitors only the time period until the last negative inhibitor result is considered for the efficacy endpoints below. Sensitivity analyses will be made only including patients who do not develop inhibitors. Further, tables will be made including only inhibitor patients. For these patients the relevant time period is the time period after positive inhibitor test.

Secondary Efficacy Endpoints

- Haemostatic effect of N8 on treatment of bleeds assessed on a predefined four point scale: Excellent, Good, Moderate and None.

The haemostatic effect of N8 will be summarised by frequency tables containing count and percentages of all bleeds.

The haemostatic effect of N8 will also be summarised by the following subgroups: Cause of bleed (Spontaneous, Traumatic, Re-bleed), Site of bleeding (Central nervous system, Haemarthrosis (Joint), Gastrointestinal, Subcutaneous, Muscular or other), Classification of bleeding (Mild/Moderate or Severe) and Time of bleeding (the day is divided into 6 time intervals, each of 4 hours). Details (cause, site, classification and time) about the bleeds will also be summarised and listed.

- Annualized bleeding rate during bleeding prevention period with N8

For this endpoint patients who develop inhibitors will only be included if they have been treated for minimum 1 month before the first positive inhibitor test. The reason to exclude these patients from the calculations is that if the treatment period is too short, the uncertainty introduced on the estimated annualized bleeding rate will be relatively large.

The annualized number of bleeds in total and by cause of bleeding (spontaneous or traumatic) will be estimated by a Poisson model allowing for over-dispersion and presented with a 95% confidence interval (CI).

In addition, the annualized number of bleeds in total and by cause of bleeding, excluding all bleeds occurring more than 72 hours after last N8 dose will be estimated by a Poisson model allowing for over-dispersion and presented together with a 95% CI.

The annualized number of bleeds in total and by cause of bleeding, excluding all bleeds occurring more than 48 hours after last N8 dose will also be estimated by a Poisson model allowing for over-dispersion and presented together with a 95% CI.

A sensitivity analysis will be made only including data related to the time periods where the patients are dosed three times weekly or every second day.

The time interval from last N8 dose to start of a bleed will be summarised. This will be done by a frequency tables dividing the time interval into the following 5 groups: ≤ 12 hrs, > 12 hrs and ≤ 24 hrs, > 24 hrs and ≤ 48 hrs, > 48 hrs ≤ 72 hrs, > 72 hrs. The time interval from last N8 dose to start of a bleed will also be illustrated graphically with time from last dose on the x-axis and number of bleedings on the y-axis.

- Number of N8 infusions required per bleed

The number of infusions of N8 required per bleed will be calculated as the number of infusions of N8 used in the time period from start of the bleed to stop of the bleed. The number of infusions will be presented using count and percentages of all bleeds.

- Total consumption of N8 per patient (prevention, treatment of bleeds and during surgery) per month and annualised value

Total consumption of N8 during the trial will be summarised and listed by patient.

- N8 consumption per bleed

The consumption of N8 (IU/kg BW/bleed) will be calculated as the consumption of N8 used from start of the bleed to stop of the bleed. The consumption will be summarised and listed by patient.

- N8 consumption during bleeding prevention period

The consumption of N8 during bleeding prevention period (IU/kg BW/month) will be calculated as the consumption of preventive N8 doses and summarised and listed by patient.

Secondary Safety Endpoints

- Frequency of adverse events and serious adverse events

All AEs and SAEs will be summarised by frequency of events and frequency of patients with any event. Similar summaries cross-classified by severity and by causal relation to trial product will also be made.

Furthermore, listings will be provided displaying all AEs and SAEs including pertinent clinical information.

- Incidence rate of high-titre inhibitors defined as inhibitor titre ≥ 5 Bethesda units/mL

Incidence rate of high-titre inhibitors will be calculated and a 1-sided 97.5% upper confidence limit will be provided based on an exact calculation for a binomial distribution.

- Incidence rate of clinically relevant inhibitors defined as an inhibitor titre (≥ 0.6 BU/mL) combined with a decreased recovery (<66% of expected level)

The incidence rate of clinically relevant inhibitors will be calculated and a 1-sided 97.5% upper confidence limit will be provided based on an exact calculation for a binomial distribution. Furthermore, the time to inhibitor development and clinically inhibitor development will be presented by a Kaplan Meyer plot.

The relationship between the incidence rate of clinically relevant inhibitors and high-titre inhibitors and different patient and treatment characteristics will also be investigated.

Outcome of inhibitor treatment will be listed and summarised.

All additional safety parameters such as laboratory parameters and physical examinations will be listed and summarised by visit for all patients.

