- Incidence rate of inhibitors defined as inhibitor titres ≥ 0.6 Bethesda units/mL *for the main phase of the trial*

The incidence rate of inhibitors will be calculated and a 1-sided 97.5% upper confidence limit will be provided based on an exact calculation for a binomial distribution. For the calculation of the incidence rate the numerator will include *number of all patients with inhibitors* while the denominator will include *number of all patients with confirmed inhibitors during the main phase of trial or completed the main phase without confirmed minimum of 50 ED plus any patients with less than 50 ED but with inhibitors*.

2.44 18.2.4 Supportive Secondary Endpoints

All the below efficacy endpoints will be evaluated for the main phase of trial, for the extension phase of trial, and for the combined main and extension phases. Sensitivity analyses will be made only including patients who do not develop inhibitors during the main phase of the trial and during the extension phase of the trial. For patients that develop inhibitors only the time period until the last negative inhibitor result is considered for the efficacy endpoints below. Sensitivity analyses will be made only including patients who do not develop inhibitors. Further, tables will be made including only inhibitor patients. For these patients the relevant time period is the time period after positive inhibitor test.

Secondary Efficacy Endpoints

- Annualized bleeding rate during bleeding prevention period with turoctocog alfa

For this endpoint patients who develop inhibitors will only be included if they have been treated *with at least two doses of trial product for minimum 1 month* before the first positive inhibitor test. The reason to exclude these patients from the calculations is *that if the treatment period is too short, that the information from the treatment with one dose is too small and the uncertainty introduced on the estimated annualized bleeding rate will be relatively large.*

Separate reports and listings will be made for the above efficacy endpoints for patients developing inhibitors. Data used in these reports and listings will include data from the first time patient is confirmed with inhibitors until the end of the main phase of trial as well as until the end of trial. Furthermore, each of these reports will also be generated for different method for management of patients with inhibitors.

Secondary Safety Endpoints

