2.39 19.1 Informed Consent Form for Trial Patients	20

2.40	19.4 Regulatory Authorities.....	21
2.41	20 Premature Termination of the Trial/Trial Site	21
2.42	23 Responsibilities	21
2.43	25 Retention of Clinical Trial Documentation.....	22
2.44	Attachment I – Global.....	22

Table of figures

	Page
Figure 12–1	17

Table of tables

	Page
Table 2–1 Visit Flow Chart main trial phase	6
Table 2–2 Visit Flow Chart trial extension phase	6

1 Introduction including rationale for the protocol amendment

The main reasons for this amendment is to re-define the duration and conditions for treatment of patients with inhibitors, restrict the number of previous exposures to blood components (to keep a homogenous PUP population), re-define the trial duration and revise the date of end of trial. In addition, the possibility to further investigate immunogenicity of turoctocog alfa e.g. non-neutralising antibodies assessment and Human Leucocyte Antigen (HLA) genotyping will be introduced. Some changes are administrative to align with updated guidelines and Novo Nordisk Standard Operation Procedures e.g. the requirement to list the participating countries has been removed.

The Patient Information and Informed Consent will be adapted accordingly.

In this protocol amendment:

- Any new text is written ***in italics***.
- Any text deleted from the protocol is written using **strike through**.
- Corrections of minor inconsistencies and ambiguities, and typographical errors will not be listed.

2 Changes

2.1 1 Summary

Trial Design

The trial consists of two phases. In the main phase, an aggregated number of at least 50 patients will receive preventive treatment with turoctocog alfa until they reach a minimum of 50 exposure days² (ED) or until they develop inhibitors. After that the patients will continue in the extension phase ~~until where at least 50 patients should achieve~~ at least 100 ED ~~has been achieved~~, which will translate into a ~~maximum~~ trial duration of up to 3.5 5 years (*including any potential inhibitor treatment*). The estimated total duration of the trial is approximately 5 7 years.

Trial Population

Approximately 60 PUP with severe (FVIII \leq 1%) haemophilia A with no history of inhibitors below 6 years of age ~~in a non-bleeding state~~ will be enrolled to allow for at least 50 patients to complete the trial

Key Inclusion Criteria

- ---

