During the course of the trial, the Monitor will visit the trial site to ensure that the protocol has been adhered to, that all issues have been recorded, to perform source data verification and to monitor drug accountability. *The first monitoring visit will be performed as soon as possible after FPFV and no later than 4 weeks after.* The visit intervals will depend on the outcome of the remote monitoring of the eCRFs, the trial site's recruitment rate, and the compliance of the trial site to the protocol and GCP, ~~but~~ and must not exceed 12 weeks *after preventive treatment has been commenced. Prior to initiation of preventive treatment monitoring should be performed when a patient has been screened and after each treatment requiring bleed.*

2.37 18.2.1 General Considerations

The main CTR will be conducted when at least 50 patients have completed the main phase of the trial (completed visit 5 or has a confirmed inhibitor). The main CTR will present data for the main phase, the extension phase and the combined main and extension phases of the trial. An updated CTR will be conducted when all patients have completed the extension phase of the trial. The updated CTR will also present data for the main phase, the extension phase and the combined main and extension phases of the trial.

2.38 18.4 Explorative Statistical Analysis for Pharmacogenetics and Biomarkers

The data from genotyping and immunogenicity assessment will be summarised using descriptive statistics.

2.39 19.1 Informed Consent Form for Trial Patients

Prior to any trial-related activity, the Investigator must give the patient and/or the patient's LAR oral and written information about the trial in a form that the patient or the patient's LAR can read and understand. This includes the use of impartial witness where required. ~~In this trial the notion of~~

~~legal representative should be understood as both parents, or legal representative(s), as defined in Member States' national laws, who consents on behalf of the child.~~

Consent: As a child is unable to provide legally binding consent, informed consent must be sought from the parents/ legal representative (see definition above) on the child's behalf. The specific and written informed consent of the parents/legal representative must be sought prior to enrolling a child in the trial. Information should be given by an experienced Investigator to each parent, or the legal representative, on the purpose of the trial and its nature.

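### Does section 18.2.4 need one fixed date to divide the efficacy data of patients who develop inhibitors?

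*Combined protocol and SAP*

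**What the plan says.** **Version 1.0, section 18.2.4**
- Main efficacy window: "For patients that develop inhibitors only the time period until the last negative inhibitor result is considered for the efficacy endpoints below".
- Inhibitor-only tables: "For these patients the relevant time period is the time period after positive inhibitor test".
- Annualised bleeding rate (ABR): inhibitor patients are included only if "they have been treated for minimum 1 month before the first positive inhibitor test".
- A sensitivity analysis restricted to patients without inhibitors is planned.

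**Amendment that introduced the extension phase, item 2.44 (section 18.2.4)**
- Efficacy endpoints are to be "evaluated for the main phase of trial, for the extension phase of trial, and for the combined main and extension phases".
- The ABR inclusion rule now requires treatment "with at least two doses of trial product" before the first positive test.
- Separate inhibitor reports use data from the time a patient is first "confirmed with inhibitors until the end of the main phase of trial as well as until the end of trial".
- The sensitivity analysis without inhibitor patients is stated again, by phase.
- The version 1.0 sentences are reprinted in the same paragraph.

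**Where the main phase ends**
- Amendment 7, item 2.1 (Summary): patients are treated to 50 exposure days (ED) "or until they develop inhibitors".
- Amendment 7, item 2.37 (section 18.2.1): the main report is due when at least 50 patients "have completed the main phase of the trial (completed visit 5 or has a confirmed inhibitor").
- Amendment 7, item 2.3 (section 5.1): the main trial phase is complete when the number of patients who have reached 50 ED or developed inhibitors is at least 50.
- Section 5.1 as changed by the extension-phase amendment (item 2.7) treats inhibitor patients as a separate cohort, evaluated as such.

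**The concern.** Section 18.2.4 names up to four events: last negative test, positive test, first positive test and first confirmation. It never says which one moves a patient's bleeds from the main tables to the inhibitor tables.

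Under the version 1.0 wording, the time from last negative to first positive test is in neither set. A patient first positive at Visit 3 could satisfy the ABR inclusion rule and still have no time to analyse.

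If the amendment deleted that cut-off, the opposite question arises. The trial-level description of the main phase in section 5.1 would let the inhibitor report overlap the main-phase analysis. The patient-level description would give the inhibitor report that ends with the main phase zero length. A patient whose inhibitor disappears continues in the extension phase, while the inhibitor report runs to the end of the trial, so his later bleeds could appear twice.

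The stake would be that two analysts place the same bleed in different tables. In an open-label single-arm trial, the choice could then be made with the bleed data in view.

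**Working it through.** The plan states no figure for this point, so there is nothing to reproduce. The check sizes the intervals and then takes each reading of 18.2.4 in turn.

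**Inputs**
- Scheduled inhibitor tests: Visit 1 (before dosing, 0 ED) and Visits 3 to 5 (section 8.2.2 as amended).
- Windows: Visit 3 at 10–15 ED, Visit 4 at 20–25, Visit 5 at 50–55 (Table 2-1 as amended).
- Expected inhibitor rate: 30–35% (section 12.5.2). Target: 50 patients.
- Confirmatory sample: preferably within 2 weeks (section 8.2.2.1).
- Inhibitor treatment: starts within 6 months and lasts at most 24 months (section 5.3.4).
- Maximum treatment: shown as 4 and 5 years in the tracked text of section 5.3. Last visit: no later than 30 June 2018 (section 7). Both are in the amendment that added Table 2-3.

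**Patients concerned.** 0.30 × 50 = 15; 0.35 × 50 = 17.5.

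**Reading A: the last-negative cut-off stands.** Interval set aside = ED at the first positive visit minus ED at the previous scheduled test.

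| First positive | Interval (ED) | Share of ED to date |
|---|---|---|
| Visit 3 | 10 − 0 = 10 to 15 − 0 = 15 | 100% |
| Visit 4 | 20 − 15 = 5 to 25 − 10 = 15 | 5/20 = 25% to 15/25 = 60% |
| Visit 5 | 50 − 25 = 25 to 55 − 20 = 35 | 25/50 = 50% to 35/55 = 64% |

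For scale, assume 15 inhibitor patients spread evenly over the three visits, with window midpoints of 12.5, 22.5 and 52.5 ED:
- ED before the first positive = 5 × (12.5 + 22.5 + 52.5) = 437.5
- ED kept = 5 × (0 + 12.5 + 22.5) = 175
- ED set aside = 262.5
- Share of all 50 patients' ED = 262.5 / (437.5 + 35 × 52.5) = 262.5 / 2275 = 11.5%

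With 17 inhibitor patients the share is 297.5 / 2228.3 = 13.4%. Unscheduled tests would shorten the intervals.

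These intervals are not small, but the inhibitor began somewhere inside each of them. Counting the interval as inhibitor-free, or as inhibitor time, would misclassify part of it. Leaving it out of both tables is defensible. The patient first positive at Visit 3 contributes neither bleeds nor time to the Poisson model, so only the reported number of patients changes. If the amended start at confirmation applies together with the old cut-off, the interval also includes the wait for confirmation. At 2 weeks that adds 2, 4, 6 or 7 ED at one, two, three or 3.5 doses a week.

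**Reading B: the cut-off was deleted.** The reprinted paragraph has a new sensitivity sentence before the old one, and new inhibitor reports that cover the old inhibitor tables. The ABR rule likewise runs the two-dose and one-month conditions together. This pattern points to replacement, with the strike-through lost when the PDF was read.
- *Main phase.* The Summary and section 18.2.1 end a patient's main phase at inhibitor development or confirmation. The sentence in section 5.1 can be read as the trial milestone. The two end points of the inhibitor reports can be read as the data cuts for the main and updated reports described in section 18.2.1. On that reading the first report does not have zero length, and it does not overlap the patient's own main-phase data.
- *ABR rule and report start.* A minimum of two doses before the first positive test is an eligibility threshold. Confirmation is the start of a reporting window. They need not share a date.
- *After clearance.* Section 5.3.4 returns the patient to the extension phase by design. His time there may appear in the extension analysis and in an inhibitor subgroup report. No analysis adds the two, and the plan already presents main, extension and combined results, which overlap in the same way.

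**How long the double presentation could last.** Take first positive at Visit 3 on weekly dosing, confirmation 2 weeks later and the slowest permitted inhibitor course:
- Time to confirmation = (10 to 15 + 2) weeks = 0.23 to 0.33 years
- Whole course = that + 0.5 + 2 = 2.73 to 2.83 years
- Time left = 4 − 2.83 = 1.17 years to 5 − 2.73 = 2.27 years

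The calendar limit cuts this back. Having 4 full years before 30 June 2018 requires a start by mid-2014, and 5 years a start by mid-2013. A patient on this course who starts after about September or October 2015 (30 June 2018 minus 2.83 or 2.73 years) has no time left, while recruitment was planned to run to Q2 2016. Continuing beyond 100 ED is also optional and may end at commercial availability. Faster clearance lengthens the time. How many patients clear is not given.

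**The case for a change.** The case for a change is that neither reading of 18.2.4 gives one date, and that statements about a separate cohort show intent without giving a data rule. The Summary lists haemostatic effect and ABR as key secondary endpoints, and about a third of patients could be concerned. The last negative result is not expressly limited to tests before the first positive. Fixing a date needs only wording, because all sample, dose and bleed dates are collected anyway.

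Part of this stands. Section 18.2.4 could say more plainly how time after an inhibitor is tabulated, and where prevention resumed after clearance is shown. The rest does not carry a change:
- Doubt about which sentences are current comes from the lost strike-through. It is not an error in the plan.
- An analyst would naturally take the last negative result before the first positive, since the sentence separates time before the inhibitor from time after it.
- A single cut at the first positive sample is a trade-off. It brings possibly inhibitor-affected time into the main ABR. Confining resumed prevention to the inhibitor reports would remove it from the analysis of the phase the patient has re-entered.
- The planned analysis of patients without inhibitors gives efficacy results that do not depend on the dividing date.

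**Conclusion.** No change to the plan follows. This is a gap in wording that analysts can fill sensibly from the cohort and phase descriptions elsewhere in the protocol, and the obvious remedy exchanges one imperfection for another. It concerns supportive efficacy endpoints, and section 18.2.1 rules out formal hypothesis testing. The primary endpoint, inhibitor incidence in the main phase, does not use these windows.

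The size depends on the reading. With the last-negative cut-off in force, 5 to 35 ED per inhibitor patient are set aside, about 11.5% to 13.4% of all main-phase ED under the even-spread assumption. Without it, some resumed prevention is shown in two places, for a time limited by the 30 June 2018 last visit. The documents do not allow the size or direction of any bias to be computed, and none has been shown.

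The conclusion assumes that the main phase is read at patient level for efficacy data, and that the sensitivity analysis without inhibitor patients is carried out as planned.

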5.3.2 Treatment of Bleeds and dose adjustment

.....

The dose for treatment of bleeds should aim at providing a post injection level of FVIII of at least 0.50 IU/mL or 50 IU/dL. ~~The bleeding pattern of the individual patient, as well as low trough levels described above, should be considered in adjustments of the preventive dose and at the Investigator's discretion.~~

The individual dose is determined by the investigator, using the recommendations in the World Federation of Haemophilia (WFH) guidelines.¹⁰

The required dosage can be determined using the following formula

Dose (IU) = weight (kg) x desired factor level (IU/dL) x 0.5

The WFH guideline¹⁰ may be used to guide dosing. FVIII activity should not fall below the lower range for the given plasma activity level (in % of normal or IU/dL) until the bleeding episode is resolved. As the guidelines are recommendations non-compliance with them will not require protocol deviations. The maximum dose per injection mentioned in this protocol must though be followed.

Table 5-1 *Guide for dosing in bleeding episodes¹*

Degree of haemorrhage	FVIII level required (%) (IU/dl)	Frequency of doses (hours)/ Duration of therapy (days)
Early haemarthrosis, muscle bleeding or oral bleeding	20-40	Repeat every 12 to 24 hours until the bleeding episode as indicated by pain is resolved or healing achieved
More extensive haemarthrosis, muscle bleeding or haematoma	30-60	Repeat injection every 12 to 24 hours for 3-4 days or more until pain and acute disability are resolved
Life-threatening haemorrhages	60-100	Repeat injection every 8 to 24 hours until threat is resolved

X¹ Novo Nordisk company core data sheet for turoctocog alfa

This formula may be used to calculate resulting factor levels:

IU/dL (or % of normal) = [Total Dose (IU)/body weight (kg)] x 2 [IU/dL]/[IU/kg]

.....

Each administered dose (mL IU-given, vial strength and time of day) as well as efficacy in treatment of bleeds will be registered in the diary and in the eCRF.

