5.3.2 Treatment of Bleeds

~~During preventive treatment, break through bleeds may occur and require extra doses of turoctocog alfa.~~ Treatment of bleeds should be started as soon as a bleed is identified. All bleeds, mild/moderate and severe, can be treated at home. For severe bleeds (see Section 8.3.1.1) the Investigator should evaluate if the patient should be seen at the clinic. All bleeds must be reported to the clinic within 24 hours from onset of the bleed.

The dose for treatment of bleeds should aim at providing a post injection level of FVIII *according to Table 5-1 of at least 0.50 IU/mL or 50 IU/dL*.

...

Each administered dose (mL given, vial strength and time of day) as well as efficacy in treatment of bleeds will be registered in the diary and in the eCRF. *All treatments (excluding ITI treatment) administered in relation to bleeds must be recorded as 'treatment of bleeds', e.g. scheduled preventive treatment administered between start and stop time of a bleed must be registered as 'treatment of bleed'.*

...

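### Infusions and IU/kg per bleed are counted by a start-to-stop window while doses are labelled by purpose, so bleed doses given after the recorded stop drop out and ITI doses inside the window are counted in

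*Combined protocol and SAP*

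**What the plan says.** Three rules govern which endpoint a dose enters (N8 is turoctocog alfa).

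- **Per-bleed endpoints (18.2.4).** Infusions per bleed are "calculated as the number of infusions of N8 used in the time period from start of the bleed to stop of the bleed". Consumption per bleed is "calculated as the consumption of N8 used from start of the bleed to stop of the bleed". Neither rule looks at why the dose was given.
- **Recording rule (5.3.2, last amendment).** "All treatments (excluding ITI treatment) administered in relation to bleeds must be recorded as" bleed treatment. The example given is that "scheduled preventive treatment administered between start and stop time of a bleed must be registered as 'treatment of bleed". The rule itself is not limited to the start-to-stop interval.
- **Preventive consumption (18.2.4).** This "will be calculated as the consumption of preventive N8 doses and summarised and listed by patient", so it goes by purpose and not by time.

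A fourth endpoint takes in everything: "Total consumption of N8 during the trial will be summarised and listed by patient".

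The diary (8.3.1 and 8.4.5) holds the purpose of each dose, its date and time, and the start and stop of each bleed. None of the amendment text available for 18.2.4 changes the three counting rules.

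**The concern.** A clock and a label will not always select the same doses, and they part company in two places.

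The first is after the recorded stop. Table 5-1 in 5.3.2 foresees repeat dosing; for more extensive bleeds it reads "Repeat injection every 12 to 24 hours for 3-4 days or more until pain and acute disability are resolved". No section ties the stop time in the diary to the last dose given for the bleed. If a caregiver writes the stop down before the course ends, the remaining doses are labelled bleed treatment, so they are not preventive. They also lie outside the window, so they are not counted for the bleed. The per-bleed figures are then too low, which flatters the product, and the consumption components need not add up to the total.

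The second is ITI. The window has no purpose filter, so an ITI infusion that falls during a bleed counts as required for that bleed, although 5.3.2 says ITI is not bleed treatment.

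At stake are two listed efficacy endpoints in 4.2: number of infusions required per bleed and IU/kg per bleed.

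**Working it through.** The plan states no figure for these endpoints, so there is nothing to reproduce. The check sets the rules side by side by type of dose and then sizes the gap.

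**Step 1. Where each dose goes**

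| Dose | Per-bleed window (18.2.4) | Label (5.3.2) | Preventive consumption | Total consumption |
|---|---|---|---|---|
| Extra dose for the bleed, inside the window | counted | bleed treatment | no | yes |
| Scheduled prophylaxis inside the window | counted | bleed treatment | no | yes |
| Dose for the bleed after the recorded stop | **not counted** | **bleed treatment** | no | yes |
| ITI dose inside the window | **counted** | **not bleed treatment** | not stated | yes |

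The rules agree on the first two rows and conflict on the last two.

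**Step 2. Doses lost after the stop**

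Inputs from Table 5-1, row for more extensive bleeds: every 12 to 24 h, for 3 to 4 days. Assumptions: first dose at the start of the bleed, and a dose given exactly at the stop is counted. Doses in the course = days × 24 / interval. Doses omitted = course minus doses at or before the stop.

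| Course | Doses | Counted, stop at 24 h | Omitted, stop at 24 h | Omitted, stop at 48 h | Omitted, stop at 72 h |
|---|---|---|---|---|---|
| 3 days, every 24 h | 3 | 2 | 1 | 0 | 0 |
| 4 days, every 24 h | 4 | 2 | 2 | 1 | 0 |
| 3 days, every 12 h | 6 | 3 | 3 | 1 | 0 |
| 4 days, every 12 h | 8 | 3 | 5 | 3 | 1 |

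If the stop is recorded at the end of the course, nothing is omitted in any row.

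**Step 3. The same in IU/kg**

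The formula in 5.3.2 is 0.5 × desired level in IU/dL, per kg. For the 30 to 60 IU/dL row this gives 0.5 × 30 = 15 to 0.5 × 60 = 30 IU/kg per infusion. With the stop at 24 h, the amount left out of consumption per bleed runs from 1 × 15 = 15 to 5 × 30 = 150 IU/kg.

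**Step 4. ITI doses counted in**

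The rationale in the last amendment for waiving the 48 h washout refers to daily dosing during ITI. On daily ITI a bleed of 48 h (assumed) would gain about 48 / 24 = 2 infusions. This touches only the separate reports for patients who develop inhibitors. For the main efficacy summaries, 18.2.4 uses such a patient's data only up to the last negative inhibitor result.

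**Step 5. Scheduled prophylaxis inside the window**

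Here the rules agree; the size is shown for completeness. Expected scheduled doses in a bleed = doses per week × hours / 168. For 24 h this is 1 × 24 / 168 = 0.14 (once weekly) to 3.5 × 24 / 168 = 0.50 (every second day). The share of preventive doses relabelled is bleeds per year × hours / 8,766, if bleeds occur independently of the dosing schedule. Four bleeds a year of 24 h give 4 × 24 / 8,766 = 1.1%. Over 1 to 12 bleeds a year and 12 to 96 h the share runs from 0.14% to 13.1%. Bleed rates and durations are assumptions; the documents give neither.

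**The case against.** **The gap may be empty.** Section 5.3.2 ties dosing to resolution: levels are to be held up until the bleed is resolved, and the row for early bleeds repeats doses until pain has resolved or healing is achieved. If caregivers record the stop at that moment, the window catches every dose. In addition, worsening at the same site within 72 h of the stop is a re-bleed (8.3.1.3) with its own window, so some doses after the stop are recovered there. Both arguments are sound, and they are why the lower end of the range is zero. They do not close the gap. The stop time is not defined by the last dose, and the sponsor's own change to the re-bleed definition, from time since treatment stopped to time since the bleed stopped, treats the two moments as different.

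**No dose vanishes, and little rides on these endpoints.** Every dose enters total consumption. The endpoints are supportive, no hypothesis is tested, and the primary inhibitor endpoint is untouched. All of this stands.

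**A stronger reading.** A reader might infer that scheduled prophylaxis given during a bleed is also miscounted, making the per-bleed endpoints and preventive consumption wrong in the opposite direction. The documents do not support this. The window counts such a dose with the bleed, 5.3.2 labels it as bleed treatment using the same start and stop, and the amendment gives consistent reporting as its reason. Whether such a dose was truly required is arguable, but the convention is deliberate and stated. Nor is any comparison of infusions per bleed between regimens planned.

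**Conclusion.** The concern holds for two types of dose. As written, 18.2.4 leaves bleed doses given after the recorded stop out of both per-bleed endpoints and out of preventive consumption, and it counts ITI doses given during a bleed as required for that bleed in the inhibitor-patient reports.

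The size cannot be fixed from the documents, because it turns on when the stop is written down. For a course of 3 to 8 doses it is 1 to 5 doses omitted with a stop at 24 h, falling to none with a stop at the end of the course. The direction for doses after the stop is known: the per-bleed figures can only be too low.

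It would go too far to call the endpoints wrong. They can be computed as defined, and if stops are recorded at the end of dosing, the first problem does not arise. The change is still worth making, because a stated rule would otherwise produce biased figures from data that already allow a better count.

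**What to change.** In 18.2.4, define infusions per bleed and IU/kg per bleed as all doses recorded as bleed treatment and assigned to that bleed by date and time. Include doses after the recorded stop and exclude ITI doses. Keep the start-to-stop count as a sensitivity table.

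State the assignment rule for doses after the stop. One workable rule is that a dose labelled as bleed treatment belongs to the most recent bleed that began before it, so that doses after the onset of a re-bleed go to the re-bleed. Add a tie-break for bleeds that overlap.

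Scheduled prophylaxis inside the window can stay with the bleed under the sponsor's convention. No new diary field is needed.

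The cost is a little programming and a short rule for doses after the stop, and the per-bleed figures may look less favourable. One further caution: the explicit recording rule came in the last amendment, so a scheduled dose given during an earlier bleed may carry the preventive label. The programming can apply the convention to those doses from their recorded times, and the sensitivity table will show whether it matters. How bleeds are treated does not change.
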